# 8.2 Procedures for Reporting AEs in the Case Report Form

All AEs (serious and non-serious) reported during the study visits will be captured on the appropriate study CRF including the description, seriousness criteria, severity, duration (onset and resolution date), causal relationship with the Syde® medical device or study procedure, actions taken, and outcome.

The outcome of each AE (serious or non-serious) should be entered with a term such as those described below:

- recovered without sequelae
- recovered with sequelae
- ongoing
- change in severity grade (worsening, improving)
- died

Template No.: RWI\_TP\_EPI0011 Revision 2 Reference: RWI\_WI\_EPI0005

ARMGO Pharma, Inc. RYR1-RM Study Version 4.0 dated 10-SEP -2024 Protocol/Study No.: CL-EPI-001 Page 52 of 64

If any of the same AEs occur on several occasions in the same participant, then the AE in question must be documented and assessed each time.

# 8.3 Procedures for Reporting Adverse Events (AEs) to Local and Regional Health Authorities

In addition to recording the event on the CRF, all SAEs and non-serious AEs considered related to the Syde® medical device or study procedure, reported during study visits may also need to be reported to local health authorities and regional bodies as per local guidelines. The participating physician is responsible for maintaining compliance with local guidelines as well as with any applicable site-specific requirements related to the reporting of SAEs or other safety information to the local IRB/IEC that approved the study.

# 9. ETHICAL AND REGULATORY CONSIDERATIONS

# 9.1 Guiding Principles

To ensure the quality and integrity of research, this study will be conducted under the guidelines for good pharmacoepidemiology practices issued by the International Society for Pharmacoepidemiology, the Declaration of Helsinki and its amendments, and any applicable national guidelines.

#### 9.2 Required Documents

Prior to the enrolment of any participants in the study, the following documents must be provided by the site to the Sponsor (or their designee):

- Copy of the IRB/IEC approval letter for the protocol and informed consent (all written information provided to the participant must be approved by the IRB/IEC);
- Copy of the IRB/IEC approved informed consent document to be used;
- Copy of the protocol signature page signed by the investigator; and
- Fully executed site agreement with Sponsor.

# 9.3 Patient Information and Informed Consent

An ICF must be signed by the participant before his or her participation in the study. The medical file for each participant should document the informed consent process and that written

Template No.: RWI\_TP\_EPI0011 Revision 2 Reference: RWI\_WI\_EPI0005

ARMGO Pharma, Inc. RYR1-RM Study Version 4.0 dated 10-SEP -2024 Protocol/Study No.: CL-EPI-001

Page 53 of 64

informed consent was obtained prior to participation in the study. A copy of each signed ICF must be provided to the participant. If applicable, it will be provided in a certified translation of the local language. All signed and dated ICFs must remain in each participant's study file and must be available for verification by study monitors at any time.

The ICF should be revised whenever there are changes to procedures outlined in the informed consent or when added information becomes available that may affect the willingness of the participant to participate. For any updated or revised ICFs, the medical file for each participant should document the informed consent process and that written informed consent was obtained for the updated/revised ICF for continued participation in the study.

# 9.4 Participant Confidentiality

To maintain participant confidentiality, each participant will be assigned a unique participant identifier upon study enrolment. This participant identifier will be used in place of participant name for data analysis and reporting. Medical record numbers or other local reference identifiers are not collected as part of the database. All parties will ensure the protection of participant personal data and will not include participant names on any study forms, reports, publications, or in any other disclosures, except where required by law. In accordance with local regulations in each of the registry countries, participants will be informed about data handling procedures and asked for their consent. Data protection and privacy regulations will be observed in capturing, forwarding, processing, and storing participant data. Every effort will be made to protect participant confidentiality in compliance with the Regulation (EU) 2016/679 of the European Parliament and of the Council of 27 April 2016 on the protection of natural persons about the processing of personal data and on the free movement of such data and repealing Directive 95/46/EC (General Data Protection Regulation).

The database will be housed at IQVIA in a physically and logically secure computer system kept by IQVIA as per a written security policy. The system meets approved, established standards for the security of health information and is validated. The system also meets the standards of the International Council for Harmonization of Technical Requirements for Pharmaceuticals for Human Use Good Clinical Practice E6 guideline (revision 2) regarding electronic study data handling and is available for audit upon request.

# 9.5 Independent Ethics Committee/Institutional Review Board

Consistent with local regulations and prior to enrolment of participants at a given site, the study protocol will be submitted together with its associated documents (e.g., ICF, information sheet) to the IRB/IEC responsible for its review. Participant enrolment will not start at any site before the Sponsor has obtained written confirmation of a favourable opinion/approval from the

Template No.: RWI\_TP\_EPI0011 Revision 2 Reference: RWI\_WI\_EPI0005

ARMGO Pharma, Inc. RYR1-RM Study Version 4.0 dated 10-SEP -2024 Protocol/Study No.: CL-EPI-001

Page 54 of 64

relevant central or local IRB/IEC. The IRB/IEC will be asked to provide documentation of the date of the meeting at which the favourable opinion/approval was given that clearly identifies the study, the protocol version, and the ICF version reviewed.

Before implementation of any substantial changes to the protocol, protocol amendments will also be submitted to the relevant IRB/IEC in a manner consistent with local regulations. Pertinent safety information will be submitted to the relevant IECs during the study in accordance with local regulations and requirements. It is the responsibility of the investigator to have prospective approval of the study protocol, protocol amendments, and ICF, and other relevant documents, if applicable, from their local IRB/IEC and provide documentation of approval to the Sponsor or IQVIA. All correspondence with the IRB/IEC should be retained in the investigator file.

Should the study be terminated early for any unanticipated reason, the investigator will be responsible for informing the IRB/IEC of the early termination.

Template No.: RWI\_TP\_EPI0011 Revision 2 Reference: RWI\_WI\_EPI0005

ARMGO Pharma, Inc. RYR1-RM Study Version 4.0 dated 10-SEP -2024 Protocol/Study No.: CL-EPI-001 Page 55 of 64

ARMGO Pharma, Inc. RYR1-RM Study Version 4.0 dated 10-SEP -2024 Protocol/Study No.: CL-EPI-001 Page 60 of 64

#### 11. APPENDIX

# 11.1 Full physical, neurological, and functional examination

The following tests will be conducted as part of the physical, neurological, and functional examination:

- MMT of key muscle movements (scored according to the MRC scale), including:
  - Neck flexor and extensor (note that neck flexion will be assessed separately as part of the tests conducted for the primary objective endpoints);
  - o Deltoideus;
  - o Biceps;
  - o Triceps;
  - Wrist flexor and extensor;
  - o Finger flexor, extensor, and spreader;
  - o Iliopsoas;
  - o Gluteus maximus;
  - o Quadriceps;
  - o Hamstrings;
  - o Tibialis anterior; and
  - o Gastrocnemius.
- Walking gait (Normal or Abnormal);
- Walking on heels (Yes or No);
- Walking on toes (Yes or No);
- Reflexes of biceps, triceps, knees, and achilles (scored as: 0 = No contraction; 1 = Decreased, but still present; 2 = Normal);
- Sensation of upper and lower extremities (Normal or Abnormal);
- High arched palate (Yes or No);
- Orthopaedic/dysmorphic features;
- Eye movements;
- Ptosis (Yes or No);
- Facial weakness (Yes or No); if Yes, further assess for:
  - o Strength of eye closure;

Template No.: RWI\_TP\_EPI0011 Revision 2 Reference: RWI\_WI\_EPI0005

ARMGO Pharma, Inc. RYR1-RM Study Version 4.0 dated 10-SEP -2024 Protocol/Study No.: CL-EPI-001

Page 61 of 64

- o Ability to whistle (Yes or No); and
- Ability to puff out cheeks (Yes or No);
- Joint hypermobility, scored using the Beighton scale (50).

Further details about the scoring and derived variables for each test conducted during the physical, neurological, and functional examination will be outlined in the SAP.

Template No.: RWI\_TP\_EPI0011 Revision 2 Reference: RWI\_WI\_EPI0005

ARMGO Pharma, Inc. RYR1-RM Study Version 4.0 dated 10-SEP -2024 Protocol/Study No.: CL-EPI-001

Page 62 of 64

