## 3. OBJECTIVES AND ENDPOINTS

## Table 1. Study objectives and endpoints

Objectives	Endpoints
Primary	
To determine the extent to which muscle strength is affected in participants with RYR1-RM with autosomal dominant mutations and describe measurements over time.	
 
Weight-scaled muscle strength as measured by QMA (measuring participant's shoulder abduction, elbow flexion and extension, and knee flexion and extension), MMT (measuring participant's neck flexion), and HHD (measuring participant's neck flexion)
 
Muscle strength will also be measured by additional tests:10-MWT, 1-Minute-Sit-to-Stand Test, and Stair Climb Test.
 

Secondary	
To determine the extent to which fatigue and physical function is affected in participants with RYR1-RM with autosomal dominant mutations.	PROMIS Fatigue, PROMIS-PF and, IPAQ questionnaire outputs.
To describe the demographic and clinical characteristics of participants with RYR1 -RM with autosomal dominant mutations in the real-world setting.	
 
Demographics and clinical characteristics (medication use including current and prior medications, medical history, full physical, neurological, and functional examination, height, weight, BMI, and vital signs).
 
Symptom diary.
 

Exploratory	
• To evaluate the Syde® device for use in participants with RYR1 -RM with autosomal dominant mutations.	Syde® device use in participants with RYR1- RM through objective assessment of activity (e.g., stride velocity when walking and climbing stairs).

10-MWT, 10- Meter Walk Test; BMI, Body mass index; IPAQ, International Physical Activity questionnaire; PROs, patient-reported outcomes; PROMIS, Patient-Reported Outcomes Measurement Information System; PROMIS-PF, Patient-Reported Outcomes Measurement Information System-Physical Function; *RYR1*-RM, Ryanodine receptor isoform 1-related congenital myopathies; QMA, Quantitative Muscle Assessment.

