#### 4.2.2 Exclusion Criteria

Patients meeting one or more of the following criteria will not be eligible for the study:

- Severe pulmonary dysfunction at Screening (FVC < 40% predicted) or evidence of pulmonary exacerbation (note that pulmonary exacerbations refer to acute worsening respiratory symptoms resulting from a decline in lung function);
- Significant cognitive impairment in the judgement of the investigator who will be unable to follow the protocol;
- Patients with progressive neurological conditions (e.g., Parkinson's disease);
- Non-ambulant patients; or
- Pregnant women.

Template No.: RWI\_TP\_EPI0011 Revision 2 Reference: RWI\_WI\_EPI0005

ARMGO Pharma, Inc. RYR1-RM Study Version 4.0 dated 10-SEP -2024 Protocol/Study No.: CL-EPI-001 Page 24 of 64

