## 4.2.3 Study Enrolment

The principal investigators (PIs) for the study will be neurologists who are routinely involved in the care and treatment of patients with *RYR1*-RM. Site selection criteria will include the projected availability of eligible patients in a 2.5-month enrolment period and the availability of the neurologist (and other site staff) to complete the assessments, case report forms (CRFs) and required study administration. Where possible, sites in each country specialised in treating RYR1-RM patients will be engaged in conducting the study. Selection criteria and basic site information (e.g., site size, investigator specialty, site type) will be collected via a site qualification survey.

Sites will assess initial eligibility for inclusion based on the patients' medical records (i.e., using information on their age, genetic diagnosis of *RYR1*-RM, and diagnosis of progressive neurological conditions). The eligibility criteria will be further assessed by a trained nurse/clinician during a telephone interview or as part of routine clinical care visits. For all eligible patients, the nurse/clinician will provide the Patient Information Sheet (PIS)/ICF to the patient for their review. If they agree to participate in the study, informed consent will be obtained from the patient (either independently or with the support of a caregiver, if required). Participants who consent to take part in the study will then be invited to attend the Screening Visit at the clinic (this may be conducted as part of their routine clinical care visits). At the Screening Visit, participants will be asked to confirm their consent to take part in the study (and sign the ICF if they have not done so already). Each site will maintain a Screening log to record the disposition of consecutive patients potentially eligible for study participation (e.g., demographic characteristics recorded in the patients' medical records), to better assess the representativeness of the sampled population.

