#### Table 8.

#### b) Demographics and clinical characteristics

Demographics and clinical characteristics that will be assessed in the study include sex, year of birth, medication use (current and prior medications), medical history, height, weight, BMI, vital signs, FVC, ECG, and full physical, neurological, and functional examination. The tests that will be conducted as part of the physical, neurological, and functional examination are part of routine care for participants with *RYR1*-RM and are outlined in Appendix 11.111.1.

All the above demographics and clinical characteristics will be assessed at the Screening Visit. Medication use will also be assessed at Visit 1, Visit 2, and End of Study Visit, and the physical, neurological, and functional examination will be repeated at the End of Study Visit.

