# 4.5.1 Screening Visit

The following data will be collected at the Screening Visit for all enrolled participants (listed in the order in which they will be collected during the visit):

- Informed consent;
- Inclusion/Exclusion (including MMT to assess muscle/motor function deficit, 10-MWT to assess ability to walk, and FVC to assess pulmonary dysfunction);
- Demographics (medical records);
- Medical history (medical records);
- Medication use (medical records);
- Vital signs and ECG (medical records or primary data collection; note that FVC will be evaluated as part of the assessment of the exclusion criteria);
- Strength measurements using QMA and HHD (note that MMT will be conducted at the start of the Screening Visit as part of the assessment of the inclusion criteria);
- 1-Minute Sit-to-Stand Test;
- 4SCT:
- Full physical, neurological, and functional examination;
- PROMIS Questionnaires;
- IPAO:
- Syde® device fitting;
- Symptom diary (initiation); and
- AE/SAE.

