# 6.2.2.2 Secondary Objective Analysis

The PROMIS Fatigue, PROMIS-PF, and IPAQ questionnaires will be scored according to their manual instructions (see Section 4.4.1.2). PRO endpoints assessed through the PROMIS Fatigue, PROMIS-PF, and IPAQ questionnaires and the symptom diary will be summarized using appropriate descriptive statistics, as outlined in Section 6.2.1.

Demographic and clinical characteristics of participants and data collected through the diary will be summarized with descriptive statistics, as outlined in Section 6.2.1. AE endpoints recorded throughout the study will also be summarized through descriptive analysis.

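### The reflex score in Appendix 11.1 has no category above normal, so the secondary clinical summary cannot separate normal from increased reflexes

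*Protocol*

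**What the plan says.** Appendix 11.1 of the protocol lists the tests in the physical, neurological and functional examination and gives response codes for most of them. For reflexes it states: "Reflexes of biceps, triceps, knees, and achilles (scored as: 0 = No contraction; 1 = Decreased, but still present; 2 = Normal". No code above normal, no other category and no free-text field is mentioned for this item.

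The appendix closes by saying: "Further details about the scoring and derived variables for each test conducted during the physical, neurological, and functional examination will be outlined in the SAP".

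The examination is part of a stated secondary endpoint. Table 1 includes it under "Demographics and clinical characteristics". Section 4.4.1.2 b) places it at the Screening Visit and adds that "the physical, neurological, and functional examination will be repeated at the End of Study Visit". Section 6.2.2.2 gives its analysis: "Demographic and clinical characteristics of participants and data collected through the diary will be summarized with descriptive statistics".

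**The concern.** A response scale should give the examiner a code for each result the test can produce. This one covers absent, reduced and normal reflexes, but has nothing for an increased one. An examiner who finds a brisk reflex must choose between a code that misdescribes it and no code at all.

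What is at stake is the accuracy of one part of the clinical description. One secondary objective is to describe the clinical characteristics of people with dominant *RYR1*-RM. If the normal category may also hold increased reflexes, its reported share cannot be read at face value. The same applies to a comparison of the two examinations. Because the loss occurs when the data are recorded, it has to be prevented before the examination takes place.

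**Working it through.** No arithmetic is needed. The check sets the possible findings against the available codes, then follows each route through the protocol's data rules.

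**Step 1: findings against codes (Appendix 11.1).**

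- Absent reflex: code 0.
- Reduced reflex: code 1.
- Normal reflex: code 2.
- Increased reflex: no code.

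There are four kinds of finding and three codes.

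**Step 2: what can happen to an increased reflex.**

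- *Entered as 2.* It is counted as normal. The table gives no sign that two different findings share the category.
- *Left blank.* Section 6.2.1 bases descriptive statistics on non-missing responses and reports the number and percentage missing. The blank would therefore be visible, but only as a missing value. The table would not show that the reflex had been tested and found increased.
- *Marked with a missing-data option.* Section 6.2.3 provides for marking a value as not applicable or not done. Neither describes a test that was done and gave a result.
- *Entered as a code outside the list.* Section 7.5 describes programmed eCRF checks for missing and out-of-range values. If these are built on the printed scale, both a blank and a 3 would be open to query.

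On each of the first three routes the summary cannot separate normal from increased. On the fourth, the value does not fit the printed scale.

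**Step 3: change over the study.** The examination takes place twice. A reflex that is normal at Screening and increased at End of Study would be recorded as 2 then 2, which reads as no change, or as 2 then missing. The reverse sequence has the same problem.

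**Step 4: can the SAP repair this?** Under Section 6.2.1 the SAP need only be final before database lock, which may be after the examinations have been done. It can regroup codes or define derived variables, but it cannot split a recorded 2 into normal and increased. The deferral in the appendix therefore does not settle the matter unless the response codes themselves are changed before collection.

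**Step 5: reach.** The item covers four reflex sites (biceps, triceps, knees, Achilles) at two visits. Section 6.2.2.2 uses the examination descriptively. No section of the protocol uses the reflex score for eligibility, for a primary endpoint or for the sample size.

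**The case against.** The strongest reply is that the protocol does not say an increased reflex must be entered as normal. Further scoring detail is left to the SAP, the eCRF is not shown, and a field can be left blank. Medical records are in most cases the source document (Section 7.2), so the finding may survive there. This stands to the extent that the protocol permits either coding as normal or leaving the item unscored. It does not remove the point, because neither route lets the planned summary show an increased reflex.

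A second reply is that scales ending at normal are common in this examination. The MRC strength grades in Table 5 also end at normal, and several items are simple yes or no answers. This is correct, and the point does not depend on reflexes being the odd item out. It depends only on whether the codes cover what the examiner may find.

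A reader might also infer that the missing grade hides a sign of another neurological disease, lets ineligible participants in and so distorts the strength and variability estimates. The documents do not support this:

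- The protocol does exclude "Patients with progressive neurological conditions (e.g., Parkinson's disease", but it does not use reflexes to apply that exclusion.
- Section 4.2.3 says: "Sites will assess initial eligibility for inclusion based on the patients' medical records". The information used there includes any diagnosis of a progressive neurological condition. Section 4.2.1 also requires a confirmed genetic diagnosis of *RYR1*-RM.
- Section 4.5.1 presents the Screening procedures as "listed in the order in which they will be collected during the visit". Both the eligibility check and the strength tests come before the full examination.

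For the same reason, a rule that an increased reflex should trigger a new eligibility check would be an addition to the protocol. It does not follow from this point.

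**Conclusion.** The point holds in a narrow form. Appendix 11.1 fixes a reflex score with no category above normal, so the secondary summary at Screening and End of Study cannot distinguish normal from increased reflexes, and the SAP cannot restore the distinction afterwards.

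Its importance is low. It affects one item of a descriptive secondary endpoint and leaves every primary strength estimate as it is. It assumes only that an examiner may find a reflex brisker than normal in some participant. The protocol gives no expected frequency, so the effect on any reported percentage cannot be estimated and may be nil. It also assumes that the eCRF follows the printed codes. If the eCRF already has a code for increased reflexes, the appendix only needs to be brought into line with it.

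**What to change.** Add a fourth code, 3 = Increased, to the reflex item in Appendix 11.1 and to the matching eCRF field, and include it in the range check for that field. Report all four levels for each reflex site at Screening and End of Study.

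The cost is one response option and one more row in the summary for each site. No extra test or visit time is needed. The change should be in place before participants are examined. For anyone already examined, a recorded 2 can be split only if the source notes describe the reflex.
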